4.1 Part 1, M8891 Single Agent, Solid Tumors

In the Part 1 of this study, M8891 will be administered as single agent in subjects with advanced solid tumors.

4.1.1 Primary Objectives

The primary objective is:

[figure not shown]
- To determine the maximum tolerated dose (MTD) of M8891 as a single agent in subjects with solid tumors.

4.1.2 Secondary Objectives

Secondary objectives are:

- To evaluate the safety profile and tolerability of M8891 as a single agent
- To investigate the PK profile of M8891 as single agent
- To assess the antitumor activity of M8891 as single agent according to Response Evaluation Criteria in Solid Tumors (RECIST) v1.1
- To determine the recommend Phase II dose (RP2D) as single agent.

CCI

4.2

Part 2, M8891 combined with Cabozantinib, mRCC

In Part 2 of this study, M8891 combined with cabozantinib will be administered in subjects with mRCC.

4.2.1

Part 2A, Dose Escalation

Table 6

Part 2A Objectives and Endpoints

Objectives	Endpoints (Outcome Measures)

Primary
 
To determine the recommended dose for expansion (RDE) (MTD, if reached) of M8891 combined with cabozantinib in subjects with mRCC, based on safety, tolerability, and antitumor activity	
Occurrence of DLTs in subjects with mRCC receiving M8891 combined with cabozantinib during the first 22-day treatment cycle (21 days of M8891 combined with cabozantinib, preceded by 1 day of M8891 alone) based on predefined set of AEs.Occurrence of TEAEs (including TEAEs leading to death or discontinuation of treatment) in subjects with mRCC receiving M8891 combined with cabozantinib. Any AEs that occur or worsen between start of study intervention and 30 days after end of study intervention will be considered TEAEs.Study clinically relevant abnormal changes in clinical laboratory measures from baseline, vital signs, ECOG performance status, and ECGs from start of study intervention to 30 days after end of study interventionObjective response according to RECIST v1.1 as assessed by Investigators

Objectives	Endpoints (Outcome Measures)

Secondary
 
• To characterize the PK profile of M8891 (single and multiple dose exposure) combined with cabozantinib in subjects with mRCC• To further assess antitumor activity of M8891 combined with cabozantinib in subjects with mRCC	
• PK parameters of M8891 in terms of C_{max}, t_{max}, AUC_{0-t} on Day 1 Cycle 1, (combined with cabozantinib, single dose)• PK parameters of M8891 in terms of C_{max}, t_{max}, AUC_{0-t} on Day 8 and Day 15 Cycle 1, and Day 1 Cycle 2 (combined with cabozantinib, multiple dose)
CC1	

[figure not shown]
AE: Adverse event; DoR: Duration of response; DLT: Dose limiting toxicity; ECG: Electrocardiogram; ECOG PS: Eastern Cooperative Oncology Group Performance Status CCI [REDACTED]; mRCC: Metastatic renal cell carcinoma; MTD: Maximum tolerated dose; PFS: Progression-free survival; PK: Pharmacokinetic; RECIST: Response Evaluation Criteria in Solid Tumors; RDE: Recommended dose for expansion; TEAE-Treatment emergent adverse event; CCI [REDACTED] CCI [REDACTED].

4.2.2 Part 2B, Expansion Cohort

Table 7 **Part 2B Objectives and Endpoints**

Objectives	Endpoints (Outcome Measures)
Primary	
• To determine recommended Phase II dose (RP2D) of M8891 combined with cabozantinib in subjects with mRCC based on antitumor activity and safety• Occurrence of study serious AEs including deaths from first dose of study intervention to 30 days after end of study intervention• Study clinically relevant abnormal changes in clinical laboratory measures from baseline, vital signs, ECOG PS, and ECGs from start of study intervention to 30 days after end of study intervention• Occurrence of TEAEs (including deaths) from start of the study intervention to 30 days after end of the study intervention• Objective response, according to RECIST v1.1 as assessed by Investigators
Secondary	
• To assess other measures of antitumor activity of M8891 combined with cabozantinib in subjects with mRCC• DoR according to RECIST v 1.1 criteria as assessed by Investigators• PFS time according to RECIST 1.1 criteria as assessed by Investigators 
• To characterize the PK profile of M8891 (single and multiple dose exposure) in subjects with mRCC• Plasma concentrations of M8891 on Day 1, Day 8 and Day 15 Cycle 1, (combined with cabozantinib, multiple dose)

CC1

AE: Adverse event; DoR: Duration of response; DLT Dose limiting toxicity; ECG: Electrocardiogram; ECOG PS: Eastern Cooperative Oncology Group Performance Status; CCI [REDACTED]; mRCC: Metastatic renal cell carcinoma; MTD: Maximum tolerated dose; PFS: Progression-free survival; PK: Pharmacokinetic; RECIST: Response Evaluation Criteria in Solid Tumors; RP2D: Recommended Phase II dose; TEAE-Treatment emergent adverse event; CCI [REDACTED]; CCI [REDACTED]

5 **Investigational Plan**

5.1 Overall Trial Design and Plan

This is a 2-part, Phase I/Ib, first in human, multicenter, open-label trial of M8891 administered daily.

Part 1 is a dose-escalation study designed to explore the safety, tolerability, PK and  profiles, and clinical activity of M8891 as a single agent in subjects with advanced solid tumors with no surgical, radiation, or systemic anticancer therapies available.

Part 2 is designed to determine the safety, tolerability, PK and antitumor activity of M8891 combined with cabozantinib in subjects with mRCC. Part 2 will be conducted in subjects with mRCC with clear cell component who have progressed to 1 or more prior therapy (Part 2A) or who have progressed to 1 or 2 lines of prior therapy (Part 2B) (Section 5.3.1.2). Part 2 of the study will be performed with a dose escalation (Part 2A) and a dose expansion (Part 2B) design. Part 2A is aimed at determining the MTD/RDE of M8891 combined with cabozantinib based on safety, tolerability, PK, and initial efficacy data.

The Part 2A of the study allows subject accrual in a staggered manner. Thus, enrollment in Part 2A can occur while Part 1 is still ongoing; however, enrollment will only be at a dose level of M8891 that has already been determined safe in Part 1 of the study.

Following Part 2A, the safety and tolerability of M8891 (at the MTD/RDE defined in Part 2A) combined with cabozantinib will be investigated in an expansion cohort (Part 2B) of approximately 30 evaluable for response subjects with mRCC for assessment of early clinical activity.

In Part 2 (Part 2A and 2B) cabozantinib will be given at the approved 60 mg FBE daily dosage with dosage adjustments to 40 or 20 mg FBE permitted to manage AEs. In Part 2A, 3 prespecified dose levels of M8891 are planned (20 mg, 35 mg and 60 mg), although the SMC may add or skip a dose, as long as it does not exceed the dose level of M8891 that has already been declared to be safe in Part 1 (Section 5.1.3.2.1) .

Each part of the study will include a Screening period of up to 28 days, a study intervention period consisting of 21-day cycles of M8891 single agent (Part 1) and M8891 combined with cabozantinib (Part 2), an End of Study Intervention visit (within 7 days), and a Safety Follow-up period of 30 (\pm 7) days. Subjects who discontinue study intervention for any reason will complete the End of Study Intervention and Safety Follow-up visits. In Part 2A, before Cycle 1 of all dose levels, subjects will receive a single dose of M8891 in the morning in fed conditions (Day -1, Cycle 1) and the PK profile of M8891 will be evaluated pre-dose, 1, 2, 3, 4, 6, 8 and 24h (Day 1, Cycle 1) after administration (Section 5.1.3.2.1). Subsequently on Day 1 Cycle 1, subjects will initiate

treatment with M8891 combined with cabozantinib QD orally every morning under fasted conditions.

Study duration per subject is approximately 8 months for Part 1, and 12 months for Part 2 including screening, treatment and follow up.

[figure not shown]
The design of this study is presented in

Figure 1 and a detailed Schedule of Assessments (SoAs) is provided in Table 1, Table 2, Table 3, Table 4, and Table 5.

Figure 1

Study Design

AE: Adverse event; DL: Dose level; FBE Free-base equivalent; MTD: Maximum tolerated dose; QD: Once daily; SMC: Safety Monitoring Committee; RP2D: Recommended Phase 2 Dose; mRCC: metastatic renal cell carcinoma; **CCI** [REDACTED].

- a. The MTD of M8891 single agent will be defined, and RP2D of M8891 single agent suggested, by the SMC.
- b. Subjects should have progressed to 1 or more previous lines of systemic anticancer therapy, excluding treatment with cabozantinib.
- c. Cabozantinib will be given at the approved 60 mg FBE daily dosage with dosage adjustments to 40 mg or 20 mg permitted to manage AEs.

CCI [REDACTED]

CCI [REDACTED]

- f. 30 subjects evaluable for response.
- g. The DLT assessment period for Part 2A is the Cycle 1 (= 22 days, 21 days of M8891 combined with cabozantinib, preceded by 1 day of M8891 alone) of study treatment. The rest of the Cycles in Part 2A are 21-day cycles of M8891 combined with cabozantinib.
- h. See Section 8.5.1 for the Bayesian two-parameter logistic regression model.

5.1.1 Screening Period

Screening will be performed within 28 days prior to first M8891 administration (Part 1 and Part 2). If there are no clinically significant findings based upon the Investigator's assessment, other than underlying tumor disease at Screening and the subject meets all the protocol-defined inclusion and none of the exclusion criteria, the subject will be considered as eligible. For dose-escalation Part 1 and Part 2A, eligible subjects screened for the next cohort will only be treated pending decision by the SMC. Subjects who fail to meet the protocol-specified criteria or who withdraw their consent during the screening period will be considered screening failures.

Subjects in Part 2 who do not meet the laboratory criteria (see Section 5.3.1) or for any reason exceed the screening period time for participation in this study (screen failure) may be rescreened once. Rescreened subjects will be assigned a new subject number.

5.1.2 Doppler Ultrasonography:

Version 2.0, including amendment 1.0, of this protocol excluded subjects with the presence of deep vein thrombosis (DVT) based on screening lower extremity Doppler ultrasonography but not on D-dimer levels. D-dimer has low specificity in the oncology setting ([Carrier 2008](#)) and therefore adds little value to the screening. Lower extremity Doppler ultrasonography was performed at screening, the D1, D8, and D15 of Cycle 1, and the D1 of each subsequent cycle (21 days) and withdraw subjects with a positive finding on lower extremity Doppler ultrasonography. Multiple guidelines recommend clinical prediction rules to estimate pretest probability of DVT before ultrasound or other imaging tests ordering. Lower extremity Doppler ultrasonography is the standard imaging test for patients suspected of having lower extremity DVT. A venous ultrasound does not exclude the presence of a pulmonary embolism or portal vein thrombosis, neither predicts their development in the future. After an unlikely clinical pretest probability of DVT based on a clinical decision rule assessment, a venous ultrasound is not appropriate for those individuals ([Needleman 2018](#)).

In the current Version 4.0 of this protocol, Part 1 has been revised such that D-dimer will no longer be monitored and the related exclusion criteria altered (See Table 1 and Section 5.3.2). In the remainder of the ongoing Part 1 and in Part 2, of this study, all subjects will have physical examination for the occurrence of venous thromboembolism (VTE), and imaging tests (e.g. lower extremity Doppler ultrasonography, chest computed tomography (CT) angiography, liver ultrasonography, or others) will be performed accordingly. Subjects with thromboembolic events in the last 6 months, requiring therapeutic anticoagulation will be excluded. Low dose aspirin for cardioprotection and low dose LMWH will be permitted (in subjects who are on a stable dose of LMWH for at least 6 months before the first dose of M8891 combined with cabozantinib, and who have had no clinically significant hemorrhagic complications from the anticoagulation regimen or the tumor).

The current clinical trial protocol (Version 4.0) has taken into consideration the updated clinical practice guidelines for VTE risk assessment in cancer patients. The NCCN guidelines describe that cytotoxic chemotherapy regimens, hormone therapy with estrogenic compounds, and

antiangiogenic agents are associated with increased VTE risk. The Khorana Predictive model for chemotherapy-associated VTE is the one recommended (Khorana 2008) for identifying cancer patients receiving chemotherapy who are at high risk for VTE. The risk factors identified by Khorana et al (Khorana 2008), which formed the basis for the risk assessment models, set the stage for prospective, confirmatory randomized clinical trials evaluating the risks and benefits of risk-targeted prophylaxis in ambulatory cancer patients receiving chemotherapy. Doppler ultrasonography is not included in the VTE Clinical Risk. American Society of Clinical Oncology (ASCO) recommends that outpatient candidates for chemotherapy should be scored according to the Khorana model or other validated scores at the time of chemotherapy initiation and periodically thereafter (Lyman 2015). The use of the Khorana Predictive model is a 2A level recommendation (moderate benefit-risk) in the NCCN guidelines. The European Society of Medical Oncology (ESMO) (Mandala 2011), and the National Institute of Health and Care Excellence guidelines (NICE) (Howard 2013) also include the Khorana Score along with other validated scores as an option to guide the decision-making regarding prophylaxis of patients receiving chemotherapy.

5.1.3 Treatment Period:

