Note: Low dose aspirin for cardio-protection and low dose low-molecular-weight heparin (LMWH) are permitted (in subjects who are on a stable dose of LMWH for at least 6 weeks)

before the first dose of study treatment, and who have had no clinically significant hemorrhagic complications from the anticoagulation regimen or the tumor)

- Current significant cardiac conduction abnormalities, QT corrected for heart rate according to Fridericia (QTcF) interval prolongation of > 450 ms for males and > 470 ms for females or cardiovascular disorders, including symptomatic congestive heart failure, unstable angina pectoris, and serious cardiac arrhythmias.

Investigational Medicinal Product: dose/mode of administration/ dosing schedule:

Part 1, M8891 Single Agent, Solid Tumors

M8891 in capsule form will be administered orally QD, according to the dose escalation schedule and as determined by the safety monitoring committee (SMC). The starting dose of initial dose escalation cohort will be 7 mg QD. A Bayesian two-parameter logistic regression model with overdose control will be used to assist the SMC with dose selection during the dose escalation part. The model incorporates nonclinical toxicity and observed DLT information from all previously completed dose escalation cohorts to provide a recommended dose for the next cohort.

Part 2, M8891 Combined with Cabozantinib, mRCC

Part 2A, Dose Escalation

M8891 in capsule form combined with cabozantinib will be administered orally QD in the morning in fasted conditions. Three pre-specified dose levels of M8891 are planned (20 mg, 35 mg and 60 mg) combined with 60 mg of cabozantinib.

A Bayesian two-parameter logistic regression model with overdose control will be used to assist the SMC with dose selection for the next cohort and to determine the MTD/RDE of M8891 combined with cabozantinib 60 mg QD for Part 2B. Dose levels may be added or skipped for others that are not part of the pre-specified but they will never exceed the dose level of M8891 that has already been declared to be safe in Part 1.

Cabozantinib will be used at the approved 60 mg-free-base equivalent (FBE) daily dosage with dosage adjustments to 40 mg FBE or 20 mg FBE permitted to manage AEs.

Part 2B, Dose Expansion

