5.3.2 Exclusion Criteria

5.3.2.1 Part 1, M8891 Single Agent, Solid Tumors

For Part 1, subjects are excluded from the study if any of the following criteria apply:

1. Eastern Cooperative Oncology Group Performance Status (ECOG PS) ≥ 2
2. Bone marrow impairment as evidenced by hemoglobin < 9.0 g/dL, neutrophil count $< 1.5 \times 10^9/L$, platelets $< 100 \times 10^9/L$. Transfusion is not allowed within 3 weeks before first dose
3. Renal impairment as evidenced by calculated creatinine clearance < 60 mL/min (according to the Cockcroft-Gault formula)
4. Liver function abnormality as defined by total bilirubin $> 1.5 \times$ ULN, or AST/ALT $> 2.5 \times$ ULN, for subjects with liver involvement AST/ALT $> 5 \times$ ULN
5. Extensive prior radiotherapy to more than 30% of bone marrow reserves, or prior bone marrow/stem cell transplantation within 5 years of study start
6. Clinically significant cardiac conduction abnormalities, including QTcF interval prolongation of > 480 ms and/or pacemaker or impaired cardiovascular function such as New York Heart Association classification score > 2
7. Thromboembolic events requiring therapeutic anticoagulation. Concomitant anticoagulation at therapeutic doses with oral anticoagulants (i.e., warfarin, direct thrombin

and Factor Xa inhibitors) or platelet inhibitors (i.e., clopidogrel) started within the last 6 months of screening.

Note: Low dose aspirin for cardio-protection and low dose LMWH are permitted (in subjects who are on a stable dose of LMWH for at least 6 weeks before the first dose of study treatment, and who have had no clinically significant hemorrhagic complications from the anticoagulation regimen or the tumor).

[figure not shown]
8. Pregnant or nursing female subject
9. Any other severe clinical condition that in the opinion of the treating physician may compromise the trial participation
10. Subjects used any investigational agents 14-28 days or 5-half-lives (whichever is shorter) of the initiating study treatment
11. History of difficulty swallowing, malabsorption, or other chronic gastrointestinal disease or conditions that may hamper compliance and/or absorption of the investigational drugs
12. Life expectancy < 3 months
13. Known hypersensitivity to the trial treatment or to one or more of the excipients used
14. Legal incapacity or limited legal capacity.

5.3.2.2

Part 2, M8891 combined with Cabozantinib, mRCC

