12. Cerebrovascular accident/stroke (< 6 months prior enrollment) or neurologic instability per clinical evaluation due to tumor involvement of the CNS.
13. Thromboembolic events requiring therapeutic anticoagulation. Concomitant anticoagulation at therapeutic doses with oral anticoagulants (i.e., warfarin, direct thrombin and Factor Xa inhibitors) or platelet inhibitors (i.e., clopidogrel) started within the last 6 months of screening.

Note: Low dose aspirin for cardio-protection and low dose LMWH are permitted (in subjects who are on a stable dose of LMWH for at least 6 weeks before the first dose of study treatment, and who have had no clinically significant hemorrhagic complications from the anticoagulation regimen or the tumor).
14. Presence of clinically significant cardiac, respiratory, or other medical or psychiatric condition that might interfere with participation in the trial or interfere with the interpretation of trial results.
15. History of allergic reactions attributed to compounds of similar chemical or biologic composition to cabozantinib or M8891.
16. An active second malignancy or evidence of disease of cancer (other than RCC) before the date of enrollment (exceptions are squamous and basal cell carcinomas of the skin and carcinoma in situ of the cervix, or malignancy that in the opinion of the Investigator, with

concurrence with the Sponsor's medical monitor, is considered cured with minimal risk of recurrence within 3 years).

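### The protocol gives two stable-dose periods for permitted low-dose LMWH, 6 months in Section 5.1.2 and 6 weeks in the Synopsis and exclusion criteria 7 and 13

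*Protocol*

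**What the plan says.** Four places in the protocol deal with LMWH at entry.

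- **Section 5.1.2 (Doppler Ultrasonography)**, in the paragraph on the current Version 4.0, covers the rest of Part 1 and all of Part 2. It allows low-dose LMWH in subjects "who are on a stable dose of LMWH for at least 6 months before the first dose of M8891 combined with cabozantinib".
- **Section 5.3.2.1, criterion 7 (Part 1)**, in its note, allows it in subjects "who are on a stable dose of LMWH for at least 6 weeks before the first dose of study treatment".
- **Section 5.3.2.2, criterion 13 (Part 2)** carries the same note with the same 6 weeks.
- **The Synopsis**, under the Part 2 key exclusions, allows it "in subjects who are on a stable dose of LMWH for at least 6 weeks" before study treatment starts.

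All four also require that the subject has had no clinically significant hemorrhagic complications.

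On earlier thromboembolic events, Section 5.1.2 says: "Subjects with thromboembolic events in the last 6 months, requiring therapeutic anticoagulation will be excluded". Criteria 7 and 13 instead begin: "Thromboembolic events requiring therapeutic anticoagulation. Concomitant anticoagulation at therapeutic doses with oral anticoagulants". Their second sentence continues to "platelet inhibitors (i.e., clopidogrel) started within the last 6 months of screening".

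**The concern.** One permission carries two durations in text that is in force at the same time. Section 5.1.2 is neither an amendment log nor superseded wording. It states its own rules on who is excluded and what is permitted, and it refers to Section 5.3.2 as though the two agreed.

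The subject matter makes this more than a typing slip. Section 3.3.3 names thromboembolic events as a toxicity reported with both cabozantinib and MetAP2 inhibitors, and says that specific exclusion criteria were written to reduce that risk. An on-study thromboembolic event leads to withdrawal from M8891 (Section 5.5.1) and to stopping study treatment (Table 12). Part 2A enrolls in cohorts of 3, so one disputed enrollment is a third of a cohort. Two sites, or a site and its monitor, could reach different answers on the same candidate.

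**Working it through.** No sample size, power or event count enters here. The check is a comparison of passages plus one unit conversion.

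**1. Stable-dose period**

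Inputs: 6 months (Section 5.1.2); 6 weeks (Synopsis, criteria 7 and 13); 1 month = 30.4375 days (SAP Section 9, conversion factors).

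- 6 months: 6 × 30.4375 = 182.6 days
- 6 weeks: 6 × 7 = 42 days
- Difference: 182.6 − 42 = 140.6, about 141 days
- Ratio: 182.6 / 42 = 4.3

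| Time stable on low-dose LMWH, no significant hemorrhage | Section 5.1.2 | Synopsis, criteria 7 and 13 |
|---|---|---|
| Under 42 days | not permitted | not permitted |
| 42 to about 182 days | not permitted | permitted |
| About 183 days or more | permitted | permitted |

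The texts disagree only in the middle row.

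**2. Anchor dose**

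Section 5.1.2 counts back from the first combination dose. The criteria count back from the first dose of study treatment.

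- Part 1: there is no combination dose, so the Section 5.1.2 clause has nothing to count from, although its paragraph opens by covering Part 1.
- Part 2A: M8891 is given alone on Day -1 and the combination starts on Day 1 (Section 5.1.3.2.1), so the anchors differ by one day.
- Part 2B: treatment starts with the combination, so the anchors coincide.

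The difference in anchor is therefore small in days. It does show that the clash in duration is cleanest for Part 2, against criterion 13 and the Synopsis.

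**3. Event window**

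In Section 5.1.2 the 6 months qualifies the thromboembolic event. In criteria 7 and 13 the event stands in its own sentence without a look-back, and the 6 months sits in the next sentence, on when oral anticoagulants or platelet inhibitors were started. Read literally, a subject whose event required therapeutic anticoagulation more than 6 months ago falls outside the Section 5.1.2 exclusion but inside the criteria. On that reading Section 5.1.2 is the stricter text for LMWH and the looser one for events, so a site could not settle both questions by always following the same section.

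**The case against.** The strongest reply is that the protocol shows which text decides eligibility. Sections 5.1.1 and 5.3 both define it by the inclusion and exclusion criteria. Section 5.1.2 is largely an account of why Doppler and D-dimer monitoring changed, and it points to Section 5.3.2. The Synopsis and both criteria agree with each other. This stands, and it limits the practical effect, since a site working from the criteria lists would apply 6 weeks. It does not remove the conflict. Section 5.1.2 is directive in its own right, and no rule says which section prevails.

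Four stronger readings are tempting, and the documents do not support them.

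- A reader might infer two competing event windows. The criteria state no rival figure. The 6 months in the following sentence could loosely be read to cover the event, although the full stop tells against that. The word requiring could also mean a current need for anticoagulation, which would not reach an old event no longer treated. This is ambiguity, not two values.
- A reader might infer that these criteria are the main protection now that scheduled Doppler has gone. Section 5.1.2 keeps physical examination for venous thromboembolism in all subjects, with imaging accordingly, and the withdrawal rules remain.
- A reader might infer that eligibility deviations cannot be classified, or that an analysis shifts. The SAP's deviation list follows the inclusion and exclusion criteria, and neither the Safety nor the Dose Escalation set depends on LMWH eligibility.
- A reader might count the SAP as a further contradiction. Item 216 of its Appendix 18.1 does word the thrombosis history differently, but that plan is version 1.0 of April 2018 and refers to protocol version 2.0. It says it will be amended if combination parts are added.

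**Conclusion.** The point holds as an internal inconsistency in an eligibility rule that bears on safety. Two stable-dose periods, about 183 and 42 days, are in force for the same permission. They treat differently any candidate who is on low-dose LMWH, has had no clinically significant hemorrhagic complications, and has been stable for between 6 weeks and 6 months. The conflict is direct for Part 2. For Part 1 it is weaker, because the Section 5.1.2 clause counts from a dose that Part 1 subjects never receive.

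The event-window point is secondary. It is unclear wording, and it matters only for thromboembolic events that required therapeutic anticoagulation.

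The number of candidates affected is not given and cannot be derived from the documents. The day counts assume the SAP's month factor. No estimate, operating characteristic or analysis set changes. The case for acting is that subjects should be selected the same way at every site, on a risk that the protocol itself singles out, at almost no cost.

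**What to change.** Reconcile Section 5.1.2 with the Synopsis and with exclusion criteria 7 and 13, so that the following read the same everywhere:

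1. one stable-dose period for low-dose LMWH;
2. one anchor dose, worded so that it exists in Part 1, Part 2A and Part 2B;
3. one statement of whether a look-back applies to the thromboembolic event itself and, if so, how long it is, kept separate from the look-back on starting anticoagulants or platelet inhibitors.

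Which values apply is a clinical decision for the sponsor, and none is proposed here. A simple way to prevent a recurrence is for Section 5.1.2 to refer to the criteria instead of restating them.

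The deviation-list wording should follow when the SAP is amended for the current protocol version. It needs no separate correction now.

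The cost is a protocol clarification with no effect on design or sample size. Version 3.0 introduced Part 2, and the Version 4.0 summary of changes says that no patient had been enrolled under Version 3.0. At that point the correction could have been made before any Part 2 subject entered.
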